3.7.1.1.2 De Novo Subjects

De novo subjects did not participate in Trial 405-201-00013 or Trial 405-201-00014; therefore, they must attend separate screening and baseline visits to allow for completion of eligibility assessments and washout of prohibited concomitant medications, if applicable (Table 3.7-3).

3.7.1.1.2.1 Screening

For de novo subjects, the screening period begins after informed consent has been obtained and will take place between Day –28 and Day –1 prior to enrollment (Visit 1). Although the screening period continues up to administration of the first dose of IMP, screening procedures should be initiated with a sufficient amount of time allotted in order to obtain laboratory results and ECG results from the central reader prior to dosing. Completion of screening activities may require more than 1 visit. All procedures outlined for screening in the Schedule of Assessments (Table 3.7-3) will be performed. Screening evaluations will include the following:

- An assessment of all inclusion and exclusion criteria will be made to determine the subject's eligibility for the trial.
- Demographic data will be recorded.
- Medical and psychiatric history will be recorded, including the DSM-5 diagnosis of ADHD using the ACDS Version 1.2 and MINI will be administeered to rule out other comorbid diagnoses.
- The investigator (or qualified designee) will complete the "Baseline/Screening" C-SSRS form.
- A physical examination including height measurements will be performed.
- Vital sign measurements will be recorded. See Table 3.4.3.2-1 for exclusions based on outcome of screening vital sign measurements.
- A standard 12-lead ECG will be performed after the subject has been supine and at rest for at least 5 minutes. The ECG is to be completed before any blood is drawn.

Confidential - Proprietary Information

- Blood samples will be collected for clinical laboratory tests, including hematology and serum chemistry (with HbA₁c and TSH and T₄). Blood will be drawn after a minimum 8-hour fast, if at all possible (see Section 3.7.4.2). See Table 3.4.3.2-1 for exclusions based on outcome of screening clinical laboratory tests. Vital sign and ECG assessments should be completed before any blood samples are collected.
- Blood samples will be drawn for HIV serology and the presence of HBsAg and anti-HCV.
- Alcohol testing will be conducted via a blood test or using a breathalyzer.
- A urine pregnancy test will be performed for all FOCBP. If the urine pregnancy test is positive, the result should be confirmed with a serum pregnancy test. Subjects with a positive serum test result will be excluded from the trial.
- Urine will be collected from all potential subjects for urinalysis and urine screen(s) for drugs of abuse. See Table 3.4.3.2-1 for exclusions based on outcome of urine drug screen(s).
- If subjects are taking disallowed medications and they are able to taper appropriately and safely, they will do so during the screening period. If medication taken is for ADHD, a minimum of 1 week off stimulants and 3 weeks off nonstimulants will be required before baseline. A complete washout schedule, including common excluded medications and herbal preparations, is provided in Section 4.1.
- AE recording will begin with the signing of the eICF for Trial 405-201-00015.

The sponsor reserves the right to utilize external quality oversight methods to ensure the validity of diagnosis, severity of illness, and other factors determining appropriateness of subject selection.

3.7.1.1.2.2 Baseline

If the subject is found to be eligible for the trial during the screening, the subject will attend a baseline visit (Visit 2) during which the following procedures will be completed prior to the subject starting open-label IMP:

- Inclusion/exclusion criteria will be verified. Review of inclusion/exclusion criteria at the baseline visit will be based on assessments performed during screening.
- Medications taken during the screening period will be reviewed and documented.
- A qualified rater will administer the AISRS.
- A qualified rater will administer the CGI-S.
- The investigator (or qualified designee) will complete the "Since Last Visit" C-SSRS form.
- Subjects will complete the AIM-A.
- CCI
- A physical examination will be performed.

Confidential - Proprietary Information

52

- Vital sign measurements will be recorded.
- A standard 12-lead ECG will be performed after the subject has been supine and at rest for at least 5 minutes. The ECG is to be completed before any blood is drawn.
- Blood samples will be collected for clinical laboratory tests (hematology and serum chemistry [including HbA₁c, TSH, and PT/INR]) after a minimum 8-hour fast. Vital sign and ECG assessments should be completed before any blood samples are collected.
- Alcohol testing will be conducted via a blood test or using a breathalyzer.
- Urine will be collected from all potential subjects for urinalysis and urine screen(s) for drugs of abuse. See Table 3.4.3.2-1 for exclusions based on outcome of urine drug screen(s).
- A urine pregnancy test will be performed for all FOCBP. The result must be negative prior to dosing. If the urine pregnancy test is positive, the result should be confirmed with a serum pregnancy test.
- Blood samples for FBR will be collected, if FBR consent was obtained.
- AEs and concomitant medications will be recorded.
- Open-label centanafadine SR will be dispensed to the subject and subjects will be instructed to take their 2 doses at approximately the same time every day starting on Day 1 (the day after the baseline visit).

3.7.1.2 Open-label Treatment Period

3.7.1.2.1 Weeks 1 and 2

Weeks 1 and 2 (\pm 3 days) will be Visits 2 and 3 for rollover subjects and Visits 3 and 4 for de novo subjects.

The following procedures will be performed at Week 1 and 2 visits $(\pm 3 \text{ days})$:

- A qualified rater will administer the AISRS.
- A qualified rater will administer the CGI-S.
- The investigator (or qualified designee) will complete the "Since Last Visit" C-SSRS form.
- Vital sign measurements will be recorded.
- A standard 12-lead ECG will be performed after the subject has been supine and at rest for at least 5 minutes. The ECG is to be completed before any blood is drawn.
- A urine pregnancy test will be performed for all FOCBP. If the urine pregnancy test is positive, the result should be confirmed with a serum pregnancy test.
- AEs and concomitant medications will be recorded.
- Drug accountability will be performed.

• Open-label centanafadine SR will be dispensed to the subject and subjects will be instructed to take their 2 doses at approximately the same time every day.

3.7.1.2.2 Weeks 4, 8, 12 and 16

Weeks 4, 8, 12 and 16 (\pm 3 days) will be Visits 4, 5, 6, and 7 for rollover subjects and Visits 5, 6, 7, and 8 for de novo subjects.

The following procedures will be performed at the Week 4, 8, 12, and 16 visits $(\pm 3 \text{ days})$:

- A qualified rater will administer the AISRS.
- A qualified rater will administer the CGI-S.
- The investigator (or qualified designee) will complete the "Since Last Visit" C-SSRS form.
- A physical examination will be performed (Week 8 only).
- Vital sign measurements will be recorded.
- A standard 12-lead ECG will be performed after the subject has been supine and at rest for at least 5 minutes. The ECG is to be completed before any blood is drawn (Weeks 4, 8, and 16 only).
- Blood samples will be collected for clinical laboratory tests (hematology and serum chemistry [including HbA₁c, and TSH]) after a minimum 8-hour fast. Vital sign and ECG assessments should be completed before any blood samples are collected (Week 8 only).
- Alcohol testing may be conducted via a blood test or using a breathalyzer (Weeks 4 and 12 only).
- Urine will be collected for urinalysis (Week 8 only).
- Urine will be collected for urine screen(s) for drugs of abuse (Weeks 4 and 12 only).
- A urine pregnancy test will be performed for all FOCBP. If the urine pregnancy test is positive, the result should be confirmed with a serum pregnancy test.
- AEs and concomitant medications will be recorded.
- Drug accountability will be performed.
- Open-label centanafadine SR will be dispensed to the subject and subjects will be instructed to take their 2 doses at approximately the same time every day.

3.7.1.2.3 Week 20

Week 20 (± 3 days) will be Visit 8 for rollover subjects and Visit 9 for de novo subjects.

The following procedures will be performed at the Week 20 visit (\pm 3 days):

• A qualified rater will administer the AISRS.

Confidential - Proprietary Information

54

- A qualified rater will administer the CGI-S.
- The investigator (or qualified designee) will complete the "Since Last Visit" C-SSRS form.
- Vital sign measurements will be recorded.
- A urine pregnancy test will be performed for all FOCBP. If the urine pregnancy test is positive, the result should be confirmed with a serum pregnancy test.
- AEs and concomitant medications will be recorded.
- Drug accountability will be performed.
- Open-label centanafadine SR will be dispensed to the subject and subjects will be instructed to take their 2 doses at approximately the same time every day.

3.7.1.2.4 Week 26

Week 26 (\pm 3 days) will be Visit 9 for rollover subjects and Visit 10 for de novo subjects.

The following procedures will be performed at the Week 26 visit (\pm 3 days):

- A qualified rater will administer the AISRS.
- A qualified rater will administer the CGI-S.
- The investigator (or qualified designee) will complete the "Since Last Visit" C-SSRS form.
- Subjects will complete the AIM-A.
- CC
- A physical examination will be performed.
- Vital sign measurements will be recorded.
- A standard 12-lead ECG will be performed after the subject has been supine and at rest for at least 5 minutes. The ECG is to be completed before any blood is drawn.
- Blood samples will be collected for clinical laboratory tests (hematology and serum chemistry [including HbA₁c, TSH, and PT/INR]) after a minimum 8-hour fast. Vital sign and ECG assessments should be completed before any blood samples are collected.
- Alcohol testing may be conducted via a blood test or using a breathalyzer.
- Urine will be collected for urinalysis and urine screen(s) for drugs of abuse.
- A urine pregnancy test will be performed for all FOCBP. If the urine pregnancy test is positive, the result should be confirmed with a serum pregnancy test.
- AEs and concomitant medications will be recorded.
- Drug accountability will be performed.
- Open-label centanafadine SR will be dispensed to the subject and subjects will be instructed to take their 2 doses at approximately the same time every day.

Confidential - Proprietary Information

55

3.7.1.2.5 Week 32

Week 32 (\pm 3 days) will be Visit 10 for rollover subjects and Visit 11 for de novo subjects.

The following procedures will be performed at the Week 32 visit (\pm 3 days):

- A qualified rater will administer the AISRS.
- A qualified rater will administer the CGI-S.
- The investigator (or qualified designee) will complete the "Since Last Visit" C-SSRS form.
- Vital sign measurements will be recorded.
- A urine pregnancy test will be performed for all FOCBP. If the urine pregnancy test is positive, the result should be confirmed with a serum pregnancy test.
- AEs and concomitant medications will be recorded.
- Drug accountability will be performed.
- Open-label centanafadine SR will be dispensed to the subject and subjects will be instructed to take their 2 doses at approximately the same time every day.

3.7.1.2.6 Week 38

Week 38 (\pm 3 days) will be Visit 11 for rollover subjects and Visit 12 for de novo subjects.

The following procedures will be performed at the Week 38 visit (\pm 3 days):

- A qualified rater will administer the AISRS.
- A qualified rater will administer the CGI-S.
- The investigator (or qualified designee) will complete the "Since Last Visit" C-SSRS form.
- Vital sign measurements will be recorded.
- A standard 12-lead ECG will be performed after the subject has been supine and at rest for at least 5 minutes. The ECG is to be completed before any blood is drawn.
- Blood samples will be collected for clinical laboratory tests (hematology and serum chemistry [including HbA₁c and TSH]) after a minimum 8-hour fast. Vital sign and ECG assessments should be completed before any blood samples are collected.
- A urine pregnancy test will be performed for all FOCBP. If the urine pregnancy test is positive, the result should be confirmed with a serum pregnancy test.
- AEs and concomitant medications will be recorded.
- Drug accountability will be performed.
- Open-label centanafadine SR will be dispensed to the subject and subjects will be instructed to take their 2 doses at approximately the same time every day.

Confidential - Proprietary Information

56

3.7.1.2.7 Week 44

Week 44 (\pm 3 days) will be Visit 12 for rollover subjects and Visit 13 for de novo subjects.

The following procedures will be performed at the Week 44 visit (\pm 3 days):

- A qualified rater will administer the AISRS.
- A qualified rater will administer the CGI-S.
- The investigator (or qualified designee) will complete the "Since Last Visit" C-SSRS form.
- Vital sign measurements will be recorded.
- A urine pregnancy test will be performed for all FOCBP. The result must be negative prior to dosing. If the urine pregnancy test is positive, the result should be confirmed with a serum pregnancy test.
- AEs and concomitant medications will be recorded.
- Drug accountability will be performed.
- Open-label centanafadine SR will be dispensed to the subject and will be instructed to take their 2 doses at approximately the same time every day.

3.7.1.2.8 Week 48

Week 48 (\pm 3 days) will be Visit 13 for rollover subjects and Visit 14 for de novo subjects.

Week 48 visit (\pm 3 days) will be conducted via telephone, web, or other acceptable means of contact. The following procedures will occur for all subjects:

• AEs and concomitant medications will be recorded.

3.7.1.2.9 Week 52/Early Termination (End of Treatment)

Week 52/ET (\pm 3 days) will be Visit 14 for rollover subjects and Visit 15 for de novo subjects.

The following procedures will be performed at the Week 52/ET visit (\pm 3 days):

- A qualified rater will administer the AISRS.
- A qualified rater will administer the CGI-S.
- The SMWQ questionnaire will be completed.

- The investigator (or qualified designee) will complete the "Since Last Visit" C-SSRS form.
- Subjects will complete the AIM-A.
- A physical examination will be performed.
- Vital sign measurements will be recorded.
- A standard 12-lead ECG will be performed after the subject has been supine and at rest for at least 5 minutes. The ECG is to be completed before any blood is drawn.
- Blood samples will be collected for clinical laboratory tests (hematology and serum chemistry [including HbA₁c, TSH, and PT/INR]) after a minimum 8-hour fast. Vital sign and ECG assessments should be completed before any blood samples are collected.
- Alcohol testing will be conducted via a blood test or using a breathalyzer.
- Urine will be collected from all subjects for urinalysis and urine screen(s) for drugs of abuse.
- A urine pregnancy test will be performed for all FOCBP. If the urine pregnancy test is positive, the result should be confirmed with a serum pregnancy test.
- AEs and concomitant medications will be recorded.
- Drug accountability will be performed.
- Subjects will be instructed not to initiate a different ADHD therapy until follow-up visit is completed 10 days after the last dose of IMP (Week 52/ET + 14 days).

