3.4.2.2 De Novo Subjects

Subjects are required to meet the inclusion criteria presented in Table 3.4.2.2-1.

| Tabl | e 3.4.2.2-1 Inclusion Criteria for De Novo Subjects |
|------|---|
| 1. | Subjects with a current primary DSM-5 diagnosis of ADHD (including predominantly inattentive presentation, hyperactive presentation, and combined presentations) as confirmed by the ACDS Version 1.2. |
| 2. | Subjects are 18 to 55 years of age, inclusive, at the time of consent. |
| 3. | Subjects have BMI of 18 to 40, inclusive. |
| 4. | Subjects are able to swallow multiple tablets. |
| 5. | Subjects are willing and able to comply with all testing and requirements as defined in this protocol. |
| 6. | Subjects are able to provide electronic informed consent to participate in the trial in accordance with the ICH GCP Guidance E6 and applicable regulations before completing any trial-related procedures. |
| 7. | Subjects are willing to discontinue all prohibited psychotropic medications (Section 4) starting from the time of signing the informed consent and up to the 10-day safety follow-up period. |
| 8. | Subjects are able to read English or Spanish well enough to understand the nature of the trial and to read and understand the written word in order to complete subject-reported outcome measures and be able to communicate effectively to be reliably rated on assessment scales; must be able and agree to comply with all protocol requirements, including the prescribed dosage regimens, discontinuation of prohibited medications, and report for regularly scheduled office visits. |

BMI = body mass index.

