3.7 Trial Procedures

Individual participation for rollover subjects who complete the trial without early withdrawal will be approximately 54 weeks, consisting of a 52-week open-label treatment period, and 10-day safety follow-up period after the last dose of IMP. Individual participation for de novo subjects who complete the trial without early withdrawal will be approximately 58 weeks, consisting of a screening period of up to 28 days, a 52-week open-label treatment period, and a 10-day safety follow-up after the last dose of IMP.

Trial assessment time points are summarized in Table 3.7-1 and Table 3.7-2 (rollover subjects from Trial 405-201-00013 or Trial 405-201-00014) and Table 3.7-3 and Table 3.7-4 (de novo subjects).

In addition to the trial assessment time points summarized (Table 3.7-1 and Table 3.7-2 for rollover subjects and Table 3.7-3 and Table 3.7-4 for de novo subjects CCI

Confidential - Proprietary Information

41

| Table 3.7-1 | Schedule of Assessme Baseline Through En | ents - Rol d of Trea | llover Subject atment | s from [| Frial 405 | 5-201-00 | 013 or 🛛 | Frial 40 | 5-201-000 | 14 - | | |
|-----------------------------------|---|-------------------------------------|--------------------------|--------------|--------------|--------------|--------------|--------------|---------------------------|---------------------|--|--|
| | Baseline | 52-Week Open-label Treatment Period | | | | | | | | | | |
| | 7-day follow-up visit from Trial 405-201-00013 or | W1& | | | | | | | | End of Treatment | | |
| | Trial 405-201-00014/ Baseline for | 2 (± 3 | W 4, 8, 12 & 16 | W 20 (± 3 | W 26 (± 3 | W 32 (± 3 | W 38 (± 3 | W 44 (± 3 | W 48 ^b (± 3 | W 52/ET | | |
| | Trial 405-201-00015 ^a | days) | (± 3 days) | days) | days) | days) | days) | days) | days) | (± 3 days) | | |
| Visit | 1 | 2 & 3 | 4, 5, 6, & 7 | 8 | 9 | 10 | 11 | 12 | 13 | 14 | | |
| ENTRANCE/HISTORY | Y | | | | | | | | | | | |
| Informed consent | Х | | | | | | | | | | | |
| Inclusion/exclusion criteria | Х | | | | | | | | | | | |
| Concomitant medication(s) | X ^c | Х | Х | Х | Х | Х | Х | Х | Х | Х | | |
| HIV/HBsAg/ anti-HCV | Х | | | | | | | | | | | |
| Urine pregnancy test ^d | Х | Х | Х | Х | Х | Х | Х | Х | | Х | | |
| SAFETY | | | · | • | • | | • | | | • | | |
| Adverse events | X ^c | Х | Х | Х | Х | Х | Х | Х | X | Х | | |
| Physical examination | X ^e | | Xf | | Х | | | | | Х | | |
| Vital signs | X ^c | Х | Х | Х | X | Х | Х | Х | | Х | | |

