^aScreening will include a washout period that can range from 7 to 28 days.

^bDosing will commence the day after the Baseline visit.

^cTelephone, web, or other acceptable means of contact.

^dIf the urine pregnancy test is positive, the result will be confirmed with a serum pregnancy test.

^ePhysical examination at screening will include height measurements.

^fWeek 8 only.

^gWeeks 4, 8, and 16 only.

^hWeeks 4 and 12 only.

ⁱAlcohol testing may be conducted via a blood test or using a breathalyzer.

CCI

Confidential - Proprietary Information

Version 4.0, 02 Jun 2020

| Table 3.7-4 Schedule of Assessments - De Novo Subjects - Follow-up | | | | | | |
|--|--|--|---|---|---|--|
| Period | Follow-up ^a | | | | | |
| | 1 (+1) days after the last dose of IMP | 2 (+1) days after the last dose of IMP | 3 (+ 1) days after the last dose of IMP | 5 (+ 1) days after the last dose of IMP | 7 (+ 2) days after the last dose of IMP | 10 (+ 2) days after the last dose of IMP |
| Visit | 16 | 17 | 18 | 19 | 20 | 21 |
| ENTRANCE/HISTORY | | | | | | |
| Concomitant medication(s) | Х | Х | Х | Х | Х | Х |
| EFFICACY | | | | | | |
| AISRS | | Х | | | Х | |
| SAFETY | | | | | | |
| Adverse events | Х | Х | Х | Х | Х | Х |
| Vital signs | | Х | | | Х | |
| SMWQ | Х | Х | Х | Х | Х | Х |
| Urine drug screen | | Х | | | Х | |
| Alcohol testing ^b | | X | | | Х | |
| C-SSRS | | X | | | X | |

^aFollow-up telephone calls will be conducted at 1, 3, and 5 days after the last dose of IMP, in-clinic visits on 2 and 7 days after the last dose of IMP, and a follow-up telephone call [or web, or other acceptable means of contact] 10 days after the last dose of IMP).

^bAlcohol testing may be conducted via a blood test or using a breathalyzer.

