3.7.1.3 Follow-up Period

All subjects, whether they complete the trial or are withdrawn prematurely for any reason, will be followed up for a safety evaluation during a 10-day follow up period (follow-up telephone calls at 1, 3, and 5 days after the last dose of IMP, in-clinic visits 2 and 7 days after the last dose of IMP, and a follow-up telephone call [or web, or other acceptable means of contact] 10 days after the last dose of IMP).

The following procedures will be performed at the 1-day, 3-day, and 5-day follow-up visit:

- The SMWQ questionnaire will be completed remotely.
- AEs will be recorded.
- Concomitant medications will be recorded.

The following procedures will be performed at the 2-day and 7-day follow-up visit:

Confidential - Proprietary Information

58

- A qualified rater will administer the AISRS.
- The SMWQ questionnaire will be completed in-clinic.
- Vital sign measurements will be recorded.
- Alcohol testing may be conducted via a blood test or using a breathalyzer.
- Urine will be collected for urine screen(s) for drugs of abuse.
- The investigator (or qualified designee) will complete the "Since Last Visit" C-SSRS form.
- AEs and concomitant medications will be recorded.

The following procedures will be performed at 10-day follow-up contact:

- The SMWQ questionnaire will be completed remotely.
- AEs and concomitant medications will be recorded.

Depending upon the type of follow-up required, other evaluations or tests may be conducted or performed.

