3.8.3.3 Documenting Reasons for Treatment Discontinuation

A subject may discontinue IMP for a number of reasons including those listed below:

- Reasons related to AE:
 - Subject decides to discontinue because of annoyance or discomfort due to a non-serious AE which is not otherwise determined to be an undue hazard
 - Continuing IMP places the subject at undue risk as determined by the investigator (eg, a safety concern that is possibly, probably, or likely related to IMP);
 - SAE
 - Other potentially IMP-related safety concerns or AEs
- Death
- Reasons unrelated to medical condition (provide detail and review AE history with subject)
- Withdrawal of informed consent (complete written withdrawal of consent form);
- Lost to follow-up
- Rash (regardless of severity or seriousness) (see Section 5.4)
- Pregnancy (see Section 5.7)
- Termination of all or part of the trial by the sponsor
- Lack of efficacy

Subjects withdrawn prior to Week 52 must complete the Week 52/ET evaluations at the time of withdrawal. In addition, all subjects who withdraw prematurely from the trial will be assessed by telephone 1, 3, and 5 days after the last dose of IMP, in the clinic 2 days and 7 days after the last dose of the IMP, and 10 days via telephone, web, or other acceptable means of contact after the last dose of the IMP. Three attempts will be made to contact the subject by telephone; in the event the site is unable to reach the subject by telephone, the site will attempt to contact the subject via certified mail or an alternative similar method where appropriate.

Meeting a screening exclusion criterion after enrollment does not require an automatic discontinuation of the subject. The investigator should assess the change for clinical significance, determine if an AE should be reported, and make a determination of subject continuation based on subject safety. The investigator will consult with the medical monitor to determine subject continuation in the trial.

If the subject discontinues IMP due to an AE, the investigator, or other trial personnel, will make every effort to follow the event until it has resolved or stabilized. Follow-up procedures in Section 5.9 must be followed. Subjects will be instructed not to start

Confidential - Proprietary Information

69

alternative ADHD therapy until Week 52/ET visit and appropriate follow-up visits are completed.

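### Section 3.7.1.2.9 gives two end points for staying off other ADHD therapy that do not agree; a site following the parenthesis would hold subjects off it at least 2 to 4 days past the last scheduled contact

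*Protocol*

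**What the plan says.** The last bullet of Protocol Section 3.7.1.2.9 sets how long a subject must wait before starting a different ADHD therapy: "until follow-up visit is completed 10 days after the last dose of IMP (Week 52/ET + 14 days". This is current procedural text.

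The other places that bear on the same period are:

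- Section 3.7.1.3: all subjects, completers and early withdrawals alike, "will be followed up for a safety evaluation during a 10-day follow up period".
- Tables 3.7-2 (rollover, Visit 20) and 3.7-4 (de novo, Visit 21): the last column is "10 (+ 2) days after the last dose of IMP". The COVID-19 Addendum, Table 1.2-2, has the same last column.
- Section 3.8.3.3, on subjects who discontinue: they are told not to start "alternative ADHD therapy until Week 52/ET visit and appropriate follow-up visits are completed". No day count is given.
- Section 3.4.2.2, de novo inclusion criterion 7: prohibited psychotropic drugs are to be stopped "starting from the time of signing the informed consent and up to the 10-day safety follow-up period".
- Section 5.9.2: active monitoring for serious and immediately reportable events runs to 10 days after the last dose.
- Section 3.7: participation for rollover subjects is "approximately 54 weeks, consisting of a 52-week open-label treatment period, and 10-day safety follow-up period", with a parallel figure of about 58 weeks for de novo subjects.

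**The concern.** One sentence states a treatment restriction twice, and the two statements name different moments. The main clause counts 10 days from the last dose and ties release to a completed follow-up contact. The parenthesis, "Week 52/ET + 14 days", counts 14 days from the visit and ties release to no contact at all.

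This is an instruction passed on to subjects, so the wording matters more than it would in background text. Sites reading different halves would tell subjects different things. A subject held to the later limit stays off other ADHD therapy after the last planned safety contact, with no scheduled assessment in the interval. The gap may be longest for early withdrawals. Section 3.1 asks only that their ET evaluations be done as soon as possible, so the visit may come some days after the last dose.

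**Working it through.** No figure in the plan reconciles the two limits, so the check is whether any permitted timing makes them equal.

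**Inputs.** Main clause: 10 days after last dose (3.7.1.2.9). Parenthesis: 14 days after Week 52/ET (3.7.1.2.9). Final contact window: 0 to +2 days (Tables 3.7-2 and 3.7-4). Week 52/ET visit window: ±3 days (3.7.1.2.9). Nominal Week 52: Day 364 (SAP Table 10-1). The lag between last dose and ET visit is not given, so the non-zero values below are assumptions.

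**Reading A: Week 52/ET is the actual visit.** Let D be the day of the last dose, k ≥ 0 the days from last dose to visit, and j = 0, 1 or 2 the days used of the contact window.

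- Final contact: C = D + 10 + j
- Parenthesis: P = D + k + 14
- Excess: P − C = 4 + k − j

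| k (days) | Final contact, days after visit | Excess of parenthesis (days) |
|---|---|---|
| 0 | 10 to 12 | 2 to 4 |
| 1 (assumed) | 9 to 11 | 3 to 5 |
| 3 (assumed) | 7 to 9 | 5 to 7 |
| 7 (assumed) | 3 to 5 | 9 to 11 |

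The smallest possible excess is 2 days (k = 0, j = 2), so the contact window does not close the gap.

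**Reading B: Week 52 is nominal Day 364, with visit and last dose both s days from it, s from −3 to +3.** The contact falls at Day 364 + s + 10 + j and the parenthesis at Day 364 + 14, so the excess is 4 − s − j.

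- s = 0: 2 to 4 days
- s = −3: 5 to 7 days
- s = +3: −1 to 1 day

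The two agree only when s + j = 4: a visit at +2 with the contact 2 days into its window, or a visit at +3 with the contact 1 day in. This reading can apply only to subjects who reach Week 52.

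**Participation totals.**

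- Rollover: (364 + 10)/7 = 53.4 weeks; with the +2 window, 376/7 = 53.7 weeks.
- De novo: (28 + 364 + 10)/7 = 57.4 weeks; with the +2 window, 404/7 = 57.7 weeks.
- With 14 days instead: 378/7 = 54.0 and 406/7 = 58.0 weeks.

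The stated totals are approximate and fit either count, so they do not settle which was meant.

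**Data collection.** Under Reading A, the main clause releases the subject on completion of the final contact and the parenthesis releases later. Neither allows a new ADHD drug before the last SMWQ and adverse-event contact. Under Reading B the order reverses in one corner only (s = +3, j = 2), by one day. SAP Section 9.1 counts adverse events up to 30 days after the last IMP day, but that window is the same whichever limit is followed, and no contact is planned in the interval where they differ.

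**The case against.** The strongest reply is that the working rule is clear without the parenthesis. The main clause ties release to completed follow-up, Section 3.8.3.3 does the same without a competing number, and follow-up is 10 days throughout the rest of the current protocol. On this view the 14 is a stray gloss, and a subject is held longer only where a site prefers it to everything else. Appendix 5 records that Amendment 1 moved the last contact from Day +14 to Day +10, so the parenthesis may simply be a remnant. That origin is an inference, and the finding does not depend on it.

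Most of this stands, and it is why the point is minor. It does not remove the contradiction: the parenthesis is current text within the instruction itself, and a site has no stated reason to disregard it.

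A reader might be tempted to infer three further things that the documents do not support:

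- *That the 54- and 58-week totals are wrong.* Both are stated as approximate and are compatible with the 10 (+2)-day schedule.
- *That the conflict distorts concomitant-drug, SMWQ or adverse-event data around the last contact.* Measured from the visit, both limits fall at or after that contact, so no such effect is shown.
- *That every treated subject loses 4 further days.* This ignores the +2 window and assumes that all sites follow the parenthesis over the main clause.

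**Conclusion.** The sentence is wrong as written: it gives two end points for one restriction that are not equivalent. Measured from the actual visit, the parenthesis runs 2 to 4 days past the last scheduled contact when the last dose is on the visit day, and 2 to 4 + k days past it when the ET visit comes k days after the last dose. Measured from nominal Week 52, the two coincide only at the late edge of the visit window.

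The excess arises only where a site follows the parenthesis, and the documents do not show how many would. The primary TEAE analysis, the SMWQ summary and the sample size are unaffected. Severity is minor; the reason to act is that the text governs what subjects are told about their treatment.

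**What to change.** Reconcile the parenthesis in Section 3.7.1.2.9 with its own main clause, with Sections 3.7.1.3 and 3.8.3.3, and with Tables 3.7-2 and 3.7-4, so that one anchor and one day count are stated. The sponsor's medical lead decides which limit applies; this review does not. Notify sites, and check whether any subject-facing material repeats the sentence (the consent text was not available for review). The participation totals need no change. The cost is a one-line protocol clarification and a site letter.
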